#### CONFIDENTIAL

214066 Protocol Amendment 02

#### **CONFIDENTIAL**

214066 Protocol Amendment 02

## PROTOCOL AMENDMENT SUMMARY OF CHANGES TABLE

DOCUMENT HISTORY							
Document	Date	Document Identifier					
Amendment 02	18 Nov 2022	TMF-15144431					
Amendment 01	22 June 2022	TMF-14729908					
Original Protocol	09 December 2021	TMF-13909650					

#### **Amendment 02** / 18 Nov 2022

This amendment is considered to be substantial based on the criteria set forth in Article 10(a) of Directive 2001/20/EC of the European Parliament and the Council of the European Union.

#### **Overall Rationale for the Amendment:**

The primary rationale for Amendment 02 is to include heart failure (HF) and esophageal/gastric erosions as adverse events of special interest (AESIs) following recent review of the clinical trial data in the adult daprodustat global development program. The description of the changes to the protocol by adding HF and esophageal/gastric erosions as an AESI are provided in the table below. Additional changes are to provide further clarity. A description and brief rationale for each change is provided in the table below.

Section # and Name	Description of Change	Brief Rationale
Section 2.3.1. Table 3 Risk Assessment	Addition of HF and esophageal/gastric erosions as potential risk of clinical significance in Table 3, with a summary of the data/rational for risk and mitigation strategy.	To add in HF and esophageal/gastric erosions as AESIs following recent review of the clinical trial data in the adult daprodustat global development program.
Section 8.3.6. Adverse Events of Special Interest	Addition of 2 new AESIs defined for this protocol	To add in HF and esophageal/gastric erosions as AESIs following recent review of the clinical trial data in the adult daprodustat global development program
Section 5.1. Inclusion Criteria	Revision of wording of inclusion criterion 4, from acceptable method of contraception, to a highly effective method of contraception.	To align with the wording in Appendix 10.4, as requested by a Regulatory Agency.
Section 4.6. Hemoglobin Target Range and Frequency of Checks	Revision to Table 11 for participants requiring temporary stop but already on the lowest dose step.	To provide guidance on dose level for restart in these scenarios.

## TMF-15144431 CONFIDENTIAL

### 214066 Protocol Amendment 02

Section 8.4.1. Integrated PK Phase	Addition of new reference.	To refer to updated guidance on blood volume sampling in minors.
Throughout protocol	Minor editorial updates	To correct spelling and formatting.

## CONFIDENTIAL

214066 Protocol Amendment 02

#### CONFIDENTIAL

214066 Protocol Amendment 02

### 1. PROTOCOL SUMMARY

## 1.1. Synopsis

#### **Protocol Title:**

An Integrated Pharmacokinetic and Safety Open-label Basket Trial of Daprodustat for the Treatment of Anemia Associated with Chronic Kidney Disease in Male and Female Children and Adolescents Aged 3 Months to Under 18 Years Requiring or Not Requiring Dialysis.

#### **Brief Title:**

Anemia Studies in CKD: Erythropoiesis via a Novel PHI Daprodustat - Pediatric (ASCEND-P)

#### **Rationale:**

Anemia associated with chronic kidney disease (CKD) affects most children with moderate to advanced CKD, occurring in 58% of patients with CKD stage 2 and increasing to 93% in patients with CKD stage 5. As in adults, anemia results primarily from impaired erythropoietin production by the failing kidneys and can be treated by interventions that restore erythropoietin deficiency.

Daprodustat has been extensively studied in adults for the treatment of anemia associated with CKD, demonstrating dose-dependent increases in hemoglobin (Hgb) in CKD patients who were not receiving erythropoiesis stimulating agent (ESA) therapy for their anemia, or the ability to effectively replace existing ESA therapy in CKD patients on prior stable therapy. Daprodustat has not been investigated in a pediatric population of renal anemia, where, despite available treatments of injectable ESA therapy and standard of care (SoC) iron supplementation, there remains an unmet medical need for alternative treatments.

The purpose of this study is to investigate the pharmacokinetics (PK), safety and efficacy (Hgb response) of daprodustat in children (aged 3 months to 11 years) and adolescents (aged 12 to 17 years) with anemia of CKD in both ESA users and non-users.\*

### **Overall Design:**

This protocol describes 2 independent, prospective, interventional, open-label, single arm trials, evaluating PK (4 weeks), safety (52 weeks) and efficacy (Hgb response over 52 weeks) of oral daprodustat in pediatric patients with CKD:

- not yet requiring dialysis (non-dialysis [ND]),
- requiring dialysis (D).

-

[figure not shown]
\* ESA users are defined as patients who received at least 1 dose of ESA in the 3 months (90 days) prior to enrollment for the treatment of anemia associated with CKD. This includes patients on a "dose hold" (zero dose) at the time of enrollment.

TMF-15144431 CONFIDENTIAL

214066 Protocol Amendment 02

Conducting separate trials in these 2 populations is a regulatory commitment. However, given that the 2 trials differ only in the degree of kidney function at entry and their dialysis status, the ND and D trials are presented as sub-trials (hereafter the ND and D sub-trial) in a master protocol. Trial stages, procedures, analyses and reporting will remain separate for the ND and D sub-trials unless otherwise specified. Operational aspects will be unified within the master protocol to promote efficiency, as shown in the figure below.

### Two Independent Sub-trials within a Master Protocol

Abbreviations: IDMC = independent data monitoring committee.

#### **Brief Summary:**

The purpose of this study is to investigate the PK, safety and efficacy (Hgb response) of daprodustat in pediatric participants aged 3 months to less than 18 years with anemia associated with CKD (who will be studied sequentially in 4 decreasing age groups: 12 to <18 years, 6 to <12 years, 2 to <6 years and 3 months to <2 years).

All eligible participants will receive daprodustat for 52 weeks. PK assessments in the first 4 weeks of dosing are required in the initially recruited subset of participants in each age group (Integrated PK Phase) for each sub-trial (ND/D). These participants, who undergo the Integrated PK Phase, continue seamlessly with further dosing in the sub-trial, but further recruitment of their age group and the opening up of recruitment in the next sequential younger age group is prohibited until the data (PK, safety and Hgb response) from each Integrated PK Phase is analyzed, and no concerns for continuing the study as planned are detected.

Concomitant SoC therapy is permitted (with the exception of erythropoietin and its analogues), including iron supplementation at the discretion of the investigator to ensure iron replete status.

TMF-15144431 CONFIDENTIAL

214066 Protocol Amendment 02

All participants who are approached for this study will already be participating in the prospective observational Cohort Study 212914, also running at the same trial sites. Participants will attend a study site visit at Screening and Day 1 (Baseline) before starting daprodustat (study intervention) at the end of Day 1 assessments. To allow flexibility, Screening and Day 1 Visits can be conducted up to 4 weeks apart but may also be performed on the same day. Blood tests for eligibility checked at Screening do not need to be repeated if the Day 1 Visit is performed within 7 days of the Screening Visit. After commencement of daprodustat, participants will be seen at Week 2 and Week 4 Visits to assess the initial safety and Hgb response to daprodustat. Further visits while participants remain on daprodustat are scheduled at 4-weekly intervals up to Week 28, then every 8 weeks up to Week 52. There is a Follow-up Visit at Week 56, 4 weeks after the last dose of daprodustat. Between Weeks 28 to 52, an extra Hgb check visit should be undertaken if a dose change has been made and the next scheduled visit is not within 4 weeks. An unscheduled (UNS) visit (at any time during the study) may be conducted if, in the opinion of the investigator, the participant would benefit from additional monitoring of Hgb sooner than the next scheduled visit (within 4 weeks) and/or for other parameters or if there is a safety concern.

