#### 1.3. Schedule of Activities

The Schedule of Activities (SoA) is presented in Table 1.

Table 1 Schedule of Activities

							Treatme	nt Period	I						gb Check lisit	Early Discontinuation	Follow -up
Procedure	Screening (-4 weeks to Day 1)	Day 1	Week 2 (± 3 days)	Week 4 (-7 to +2 days)	Week 8 (-7 to +2 days)	Week 12 (-7 to +2 days)	Week 16 (-7 to +2 days)	Week 20 (-7 to +2 days)	Week 24 (-7 to +2 days)	Week 28 (-7 to +2 days)	Week 36 (-7 to +2 days)	Week 44 (-7 to +2 days)	Week 52 (-7 to +2 days)	UNS at Any Time Day 1 to Week 56 a	4-weekly if needed (Weeks 32, 40 & 48) b	from Study Intervention / Withdrawal Visit	Week 56 (-7 to +2 days)
Informed consent	Х																
ELIGIBILITY ASS	SESSMENTS																
Inclusion and exclusion criteria	х	Х															
Demography	Х																
Medical and treatment history	Х																
12-lead ECG c	Х																
SAFETY ASSESS	SMENTS																
AE/SAE assessment	Х	Х	Х	Х	Х	Х	Х	Х	Х	Х	Х	Х	Х	Х	Х	Х	х
Vital signs (BP, HR) d	Х	Х	Х	Х	Х	Х	Х	Х	Х	Х	Х	Х	Х	Х	Х	Х	Х
Height, weight e	Х	Х	Х	Х	Х	Х	Χ	Х	Х	Χ	Х	Х	Х	Х	Х	Х	Х
Physical exam	Х	Х				Χ			Х		Х		Х	X a		Х	Х

214066 Protocol Amendment 02

							Treatme	nt Period	I					Extra Hgb Check Visit		Early Discontinuation	Follow -up
Procedure	Screening (-4 weeks to Day 1)	Day 1	Week 2 (± 3 days)	Week 4 (-7 to +2 days)	Week 8 (-7 to +2 days)	Week 12 (-7 to +2 days)	Week 16 (-7 to +2 days)	Week 20 (-7 to +2 days)	Week 24 (-7 to +2 days)	Week 28 (-7 to +2 days)	Week 36 (-7 to +2 days)	Week 44 (-7 to +2 days)	Week 52 (-7 to +2 days)	UNS at Any Time Day 1 to Week 56 a	4-weekly if needed (Weeks 32, 40 & 48) b	from Study Intervention / Withdrawal Visit	Week 56 (-7 to +2 days)
Tanner staging		Х											Х			Χf	
LABORATORY	ASSESSMEN	TS		•	•	•	•	•	•		•	•					
Hgb (full blood count)	Х	Х	Х	Х	Х	Х	Х	Х	Х	Х	Х	Х	Х	X g	Х	Х	Х
Iron parameters (TSAT, ferritin)	Х	Х		Х	Х	Х	Х	Х	Х	Х	Х	Х	Х	X g	X g	X	Х
Creatinine, urea/BUN, potassium, sodium, calcium	Х	Х		Х	Х	Х	Х	Х	Х	Х	Х	Х	Х	X a	X a	Х	Х
LFTs (+INR h)	Х	Х		Х	Х	Х			Х		Х		Χ	X g	X g	Х	Х
Pregnancy test (FOCBP only) i, l	Х	Х	Х	Х	Х	Х	Х	Х	Х	Х	Х	Х	Х	X g	X g	Х	Х
PK Sampling (Optional unless in the Integrated PK Phase)		Χj	X k	X k													

214066 Protocol Amendment 02

							Treatme	nt Period							gb Check isit	Early Discontinuation	Follow -up

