#### NOTE:

- All visit timings are relative to Day 1. Daprodustat will be dispensed to cover the visit period (plus permitted time window) at each dispensing visit. An IRT transaction will be
  required to dispense daprodustat. Additional IRT transactions may occur to dispense additional daprodustat in case replacement is needed.
- Blood tests for eligibility checked at Screening do not need to be repeated if the Day 1 Visit is performed within 7 days of the Screening Visit.
- All Day 1 procedures will be before the first of dose of daprodustat, except for post dose PK sampling on Day 1 (which occurs at the end of Day 1 once a participant is confirmed
  as eligible and is enrolled into the study). PK sampling is required for those participants in the Integrated PK Phase, otherwise PK sampling is optional.
- a. An unscheduled (UNS) /extra check Hgb Visit may be conducted at any time during the study if, in the opinion of the investigator, the participant would benefit from additional monitoring of Hgb and/or other parameters if clinically indicated.
- From Week 28, an extra Hgb check Visit should be arranged 4 weeks after the last dose visit if:
  - At the last study visit:
    - o there was a dose change
    - o if dosing was temporarily withheld as Hgb >12.5 g/dL
    - o a dose reduction was needed but the participant was on lowest dose already
  - Since the last study visit the following occurred:
    - o a moderate CYP2C8 was prescribed
    - o a rhEPO or analogue was given in error
    - o a Hgb check performed outside of the study indicates a dose change is needed
  - In the opinion of the investigator the participant would benefit from continued 4-weekly Hgb checks:
    - o as the Hgb is at the upper end of the target range
    - waiting 8 weeks for the next Hgb check is considered too long.
- c. If prolonged QT/QTcF is noted, 2 additional ECG measurements should be obtained and the average QT/QTcF of the triplicate assessment used for eligibility determination. No further ECG monitoring is required, unless as indicated as part of routine care of a participant, see Section 8.2.3.
- d. BP and HR will be assessed with using an appropriate size cuff. BP and HR should be preceded by at least 5 minutes of rest for the participant in a quiet setting without distractions. Three consecutive BP measurements will be obtained, of which the median will be recorded.

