#### CONFIDENTIAL

214066 Protocol Amendment 02

Dose adjustment	Hgb status
To the next lower dose	
 
If the Hgb is >12.0 but ≤12.5 g/dL.         OR
 
the Hgb increased by >2.0 g/dL in 4 weeks.         OR
 
the Hgb increased by >1.0 g/dL in 2 weeks.         Note: if the participant is already on the lowest dose step and requires a dose reduction, withhold dosing and re-check Hgb in 4 weeks, dosing should restart at the lowest dose step when the Hgb is ≤12.0 g/dL.
 

To temporarily stop	If the Hgb is >12.5 g/dL, temporarily withhold dosing and check Hgb at the next study visit in 4 weeks.  Restart at the next lower dose when the Hgb is ≤12.0 g/dL.  Note: From Week 28 if the next study visit is more than 4 weeks from date of test, schedule an extra Hgb check Visit in 4 weeks.  Note: if the participant is already on the lowest dose step at the time of the temporary stop, dosing should restart at the lowest dose step at the next study visit when the Hgb is ≤12.0 g/dL.
No change	Otherwise maintain at the same dose.

The SoA (see Section 1.3) up to Week 28 requires visits every 4 weeks, where Hgb is checked. From Week 28 until Week 52 (when daprodustat treatment ceases), an extra Hgb Visit (at Week 32, 40 or 48) should be conducted 4 weeks after the previous study visit, if any of the following apply:

- At the previous study visit:
  - o A dose change was required (see Table 11).
  - O Dosing was temporarily withheld as follows:
    - Hgb >12.5 g/dL (see Table 11), or
    - the participant was already on the lowest dose in the dose adjustment algorithm and a dose reduction was required (see Table 11 and Section 4.5).
- The following occurs and the next study visit is not due within 4 weeks and a:
  - o Moderate CYP2C8 inhibitor has been prescribed (see Section 6.8).
  - o rhEPO or analogue has been administered in error (see Section 6.8.3).
  - Hgb check performed outside of the study (routine SoC or emergency) indicates that a dose change is needed (see Table 11).
- In the opinion of the investigator, the:
  - o Participant would benefit from continued 4-weekly Hgb checks.
  - Hgb is at the upper end of the target range and waiting 8 weeks for the next Hgb check is considered too long.

In addition to the above, an unscheduled (UNS) Visit at any time during the study may be conducted if, in the opinion of the investigator, the participant would benefit from

214066 Protocol Amendment 02

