## 8.3.1. Time Period and Frequency for Collecting AE and SAE Information

All AEs and SAEs will be collected from the signing of informed consent until the follow-up visit (Week 56) at the time points specified in the SoA (Section 1.3).

All SAEs will be recorded and reported to the sponsor or designee immediately and under no circumstance should this exceed 24 hours, as indicated in Appendix 3. The investigator will submit any updated SAE data to the sponsor within 24 hours of it being available.

Investigators are not obligated to actively seek information on AEs or SAEs after the conclusion of the study participation. However, if the investigator learns of any SAE, including a death, at any time after a participant has been discharged from the study, and he/she considers the event to be reasonably related to the study intervention or study participation, the investigator must promptly notify the sponsor.

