### 8.3.5. Pregnancy

Details of all pregnancies in female participants will be collected after the start of study intervention and until 30 days after the last dose of study intervention.

If a pregnancy is reported, the investigator will record pregnancy information on the appropriate form and submit it to GSK within 24 hours of learning of the female participant's pregnancy. While pregnancy itself is not considered to be an AE or SAE, any pregnancy complication or elective termination of a pregnancy for medical reasons will be reported as an AE or SAE.

Abnormal pregnancy outcomes (e.g., spontaneous abortion, fetal death, stillbirth, congenital anomalies, ectopic pregnancy) are considered SAEs and will be reported as such.

TMF-15144431 CONFIDENTIAL

214066 Protocol Amendment 02

The participant will be followed to determine the outcome of the pregnancy. The investigator will collect follow-up information on the participant and the neonate, and the information will be forwarded to the sponsor.

Any post-study pregnancy-related SAE considered reasonably related to the study intervention by the investigator will be reported to the sponsor. While the investigator is not obligated to actively seek this information in former study participants he or she may learn of an SAE through spontaneous reporting.

Any female participant who becomes pregnant while participating in the study will discontinue study intervention (Section 7.1).

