#### 8.2. **Key Definitions**

- Baseline value for any laboratory parameter or vital sign is defined as the last non-missing value prior to the start date and time of the study drug.
- Study day is calculated as the date of event/assessment/specimen collection the first dose of the study drug. One day will be added if resulting study day  $\geq 0$ .
- Duration of any event is defined as end date of the event start date of the event + 1.
- Duration of any event in weeks is defined as (end date of the event start date of the event + 1) / 7, rounded to one decimal place.
- Duration of any event relevant to PK analysis is defined as end date and time of the event start date and time of the event displayed in the format of HHMMSS.
- Change from baseline = post-baseline value baseline value
- Percent change from baseline = (post-baseline value baseline value) / baseline value \* 100
- Pre-treatment phase is defined as any time point prior to the first dose of the study drug, i.e., date <
 date of the first dose.
- On-treatment phase is defined as any time point on or after the first dose of the study drug and on or prior to the last dose of the study drug + 1 day, i.e., date of the first dose ≤ date ≤ date of the last dose + 1 day.
- Integrated PK Phase is defined as the first 4 weeks of dosing in the initially recruited subset of participants in each age group (a minimum of 4 participants per age group; aiming for

This document is confidential

27

SAP Version: SAP V1.0 23-Jan-2025

Effective Date 31-Aug-2020 Controlled Document ID: CC

Page 27 of 59

Statistical Analysis Plan for Interventional Studies

Sponsor: GlaxoSmithKline Research & Development Limited; Protocol No.: 214066/Protocol Amendment 02

approximately 10, 6, 4 and 4 participants for the age groups 12 to <18 years, 6 to <12 years, 2 to <6 years and 3 months to <2 years respectively), during which PK assessments are required.

Post-treatment follow-up phase is defined as any time point within 4 weeks off treatment, i.e., date
of the last dose + 1 day < date ≤ date of the last dose + 28 days.

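### The follow-up visit is described as 4 weeks after the last dose, but its Day 1 window lets it fall as early as 19 days after; nothing is scheduled to reach the 30-day pregnancy collection point

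*Protocol*

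**What the plan says.** The Brief Summary in Protocol 1.1 states: "There is a Follow-up Visit at Week 56, 4 weeks after the last dose of daprodustat". Protocol 1.1 (Intervention Groups and Duration) and 4.1 repeat the 4-week off-treatment period.

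Table 1 in Protocol 1.3 heads the two relevant columns "Week 52 (-7 to +2 days" and "Week 56 (-7 to +2 days". The first note to the table gives the anchor: "All visit timings are relative to Day 1". It adds that the drug supplied covers the permitted window. Dosing runs to the Week 52 visit; Protocol 4.6, below Table 11, says "From Week 28 until Week 52 (when daprodustat treatment ceases". SAP 4.6 reproduces the same table and notes.

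Three activities depend on the last visit or the last dose:

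- **Adverse events.** Protocol 8.3.1: "All AEs and SAEs will be collected from the signing of informed consent until the follow-up visit (Week 56".
- **Pregnancy tests.** Protocol 5.1 (criterion 4) and 8.2.5 place a test at each visit, the last at Week 56.
- **Pregnancy information.** Protocol 8.3.5: "Details of all pregnancies in female participants will be collected after the start of study intervention and until 30 days after the last dose". Criterion 4 sets the contraception commitment to at least the same 30 days.

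SAP 8.2 labels an analysis phase: "Post-treatment follow-up phase is defined as any time point within 4 weeks off treatment". That phase closes at last dose plus 28 days. Neither document ties the Week 56 visit to the actual last dose or sets a minimum time off drug.

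**The concern.** Two visits that each move independently around a Day 1 anchor do not preserve the interval between them. If Week 52 is late and Week 56 is early, the off-drug period shrinks although every visit is on schedule. The text promises 4 weeks of observation after stopping; the schedule does not secure it. At stake is the completeness of safety observation after stopping: a non-serious event arising in the fourth week off drug could go unsought, and nobody would see a deviation.

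The pregnancy point is separate and does not depend on the window. The protocol wants pregnancy information for 30 days after the last dose, but its last scheduled occasion for obtaining it is nominally day 28.

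**Working it through.** **Inputs.** Anchor Day 1 and windows of -7 to +2 days for Weeks 52 and 56 (Protocol Table 1 and notes); last dose at the Week 52 visit (Protocol 4.6; an assumption about the exact day, varied below); 28 days (Protocol 1.1, 4.1) and 30 days (Protocol 5.1, 8.3.5).

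**Calendar.** With Day 1 as day 1, Week k is day 7k + 1.

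- Week 52 = 7 × 52 + 1 = day 365; window 358 to 367.
- Week 56 = 7 × 56 + 1 = day 393; window 386 to 395.

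**The plan's own figure.** 393 − 365 = 28 days, so the stated 4 weeks is reproduced for nominal dates.

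**Permitted range, last dose on the day of the Week 52 visit.**

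- Minimum: 386 − 367 = 19 days.
- Week 52 nominal and Week 56 at its earliest: 386 − 365 = 21 days.
- Maximum: 395 − 358 = 37 days.
- If the last dose is taken the day before a Week 52 visit at +2, the minimum is 386 − 366 = 20 days.

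**Shortfalls.** 28 − 19 = 9 days against the stated 4 weeks. Against the 30-day pregnancy collection period: 30 − 28 = 2 days at nominal timing and 30 − 19 = 11 days at the minimum.

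**How many schedules are affected.** Each visit has 10 permitted days, giving 10 × 10 = 100 pairs. Of these, 45 give fewer than 28 days and 64 fewer than 30; one gives 19. This counts pairs and does not forecast when visits will happen.

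**Effect on total adverse event observation.** For on-schedule participants it ends between day 386 and day 395, a spread of 9 days; 9 / 393 = 2.3%.

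**Would re-anchoring alone be enough?** The same window around last dose + 28 gives 28 − 7 = 21 to 28 + 2 = 30 days. It would not; the early side must also go.

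**Does a 28-day minimum fit the present window?** Last dose on day 358: 358 + 28 = 386. Last dose on day 367: 367 + 28 = 395. These are the two ends of the existing Week 56 window, so a compliant day always exists. In the latest case it is a single day.

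**Does a 30-day minimum fit?** 358 + 30 = 388 and 367 + 30 = 397. The latter is 2 days beyond the present window and 4 days after nominal Week 56.

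**The case against.** The strongest reply is that Week 56 and 4 weeks are nominal times and Table 1 merely gives their tolerance. That is fair as to the 19-day extreme, which is one pair in 100. But the tolerance is set without regard to the last dose, and 45 of the 100 pairs fall below the stated 4 weeks, so the gap is not confined to that corner.

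A reader might infer more than the documents support:

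- **That the primary endpoint is materially distorted**, because off-drug time varies about two-fold (19 to 37 days). The estimand in Protocol 3.2 and SAP 7.1 counts events from Day 1 to 56 weeks, not over a fixed time off drug. Events leading to discontinuation are counted only to Week 52. Early stoppers stay to Week 56 where possible (Protocol 7.1), so unequal off-drug time is already accepted.
- **That late events are lost from the analysis**, because a visit at day 37 lies outside the SAP 8.2 follow-up phase. SAP 10.1.1 defines treatment emergence with no upper cut, SAP 8.5 uses visits as recorded, and no listed output uses that phase.
- **That adverse event collection or the last test breaches a 30-day rule.** The 30 days attach to contraception and to collecting pregnancy information. No section requires a test at day 30 or extends adverse event collection to it, and Protocol 8.3.5 does not tie collection to a visit.
- **That laboratory follow-up is cut short.** Protocol 8.2.4 covers abnormal values during participation or up to 4 weeks after the last dose, so the duty outlasts the final visit.

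Existing provisions also narrow the loss. Serious events and events of special interest are followed to resolution or stabilization (Protocol 8.3.3), and related serious events learned of after discharge must be reported (8.3.1). But 8.3.1 also says investigators need not actively seek events once participation ends, so new non-serious events in the last days remain exposed.

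**Conclusion.** The inconsistency is real and modest in effect. For a treatment completer on schedule, the final visit, the end of active adverse event collection and the last scheduled pregnancy test can come 19 to 37 days after the last dose. The stated 4-week follow-up can thus be up to 9 days short without a deviation. Independently, no scheduled contact is sure to reach the 30-day pregnancy collection point, and a nominal Week 56 visit stops 2 days before it.

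This rests on dosing continuing to the Week 52 visit; a last dose one day earlier raises the minimum to 20 days. It does not apply to participants who stop treatment early and remain to Week 56, whose interval is longer. The consequence for primary adverse event incidence is small, and SAP 8.2 needs no change. Practical reach is limited: the population PK analysis plan filed with the SAP (its section 1.1) reports only 4 adolescents enrolled, who were to continue to the protocol-defined end.

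**What to change.** In Protocol Table 1, and its copy in SAP 4.6, add that for treatment completers the Week 56 visit takes place no earlier than 28 days after the actual last dose. This always leaves a permitted day inside the existing window (days 386 to 395). Because only one day may remain, widen the late side by a few days, for example to +7 (393 + 7 = day 400).

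Reconcile Protocol 5.1, 8.2.5 and 8.3.5 by stating how pregnancy information is obtained at 30 days: either place the visit itself at or after 30 days from the last dose (earliest day 388 to 397, inside a +7 window), or keep it at 28 days or later and add a brief contact at or after day 30.

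**Cost.** Sites lose the early final visit and some participants finish a few days later. With a 28-day minimum and a +7 late side, off-drug follow-up runs from 28 to 400 − 358 = 42 days. The spread in total observation rises from 9 to 400 − 386 = 14 days (14 / 393 = 3.6%). The later visits pass nominal Week 56 by up to 7 days, against 2 now, so the wording of the estimand period should say that it runs to the follow-up visit.
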